**Study 111-301 Statistical Analysis Plan****19 IMMUNOGENICITY ASSESSMENT**

Serum samples for anti-drug antibody (ADA) tests will be drawn pre-dose on Day 1, Week 13, Week 26, Week 39, Week 52 and the Safety Follow-up or Early Termination visit. Blood (serum) samples for testing drug-specific IgE will be drawn on Day 1 and in the event of a Grade 3 or significant hypersensitivity adverse event, or at the investigator's discretion.

ADA tests will include anti-BMN 111 total antibody (TAb); TAb cross-reactive with endogenous CNP, BNP or ANP; and anti-BMN 111 neutralizing antibody (NAb).

NAb testing and TAb testing for cross-reactivity with endogenous CNP, ANP or BNP will be performed only on baseline and TAb positive samples. NAb testing will not be performed if the TAb is negative. A listing for each ADA test will be provided.

Summary tables will include all safety events up to 30 days following treatment discontinuation. **PI** [REDACTED].

The immunogenicity population will be used for all summaries. The data conversion rules for immunogenicity analysis are listed below:

	Study 111-301 Statistical Analysis Plan
---	--

Operational Data Conversion Table for Immunogenicity Analysis

Assay	Result Type	Result = "Concentration (Titer Units)"	Pos/Neg for Incidence Table	Numerical Value for Display	Numerical Value for Calculation
Anti-BMN111 TAb	Numeric Titer	Negative Screen	Negative	1	0
		Negative Immunodepletion	Negative	1	0
		Negative Titer (≤ 10)	Negative	1	0
		* Value * (e.g. 20, 30, ...)	Positive	e.g. 20, 30, ...	e.g. 20, 30, ...
		Imputed values - none MRD of assay: 10			
Anti-BMN111 NAb	Numeric Titer	Negative Screen	Negative	1	0
		Negative Immunodepletion	Negative	1	0
		Negative Titer (≤ 5)	Negative	1	0
		* Value * (e.g. 10, 20, ...)	Positive	e.g. 10, 20, ...	e.g. 10, 20, ...
		Imputed values – if TAb negative then impute result as 'Negative' for same study visit MRD of Assay: 5			
ANP Reactivity	Binary	Negative Screen	Negative		
		Negative Immunodepletion	Negative		
		Positive Immunodepletion	Positive		
		Imputed values – if TAb negative then impute result as 'Negative' for same study visit			
BNP Reactivity	Binary	Negative Screen	Negative		
		Negative Immunodepletion	Negative		
		Positive Immunodepletion	Positive		
		Imputed values – if TAb negative then impute result as 'Negative' for same study visit			
CNP-22 Reactivity	Binary	Negative Screen	Negative		
		Negative Immunodepletion	Negative		
		Positive Immunodepletion	Positive		
		Imputed values – if TAb negative then impute result as 'Negative' for same study visit			

The incidence [n(%)] of TAb titer positive results will be summarized for each scheduled visit, and overall (described as 'Ever Positive') as follows:

$$\frac{\text{Number of subjects with a positive test result}}{\text{Number of subjects with non – missing TAb result}} * 100$$

The incidence [n(%)] of NAb positive test results, and positive cross-reactivity results for ANP, BNP and CNP, will also be calculated based on the number of subjects with a non-missing TAb result, and summarized at each scheduled visit and overall.

The absolute values (numerical values) of TAb titers and NAb titers will be summarized (n, mean, SD, median, 25th and 75th percentile, minimum, maximum) at Day 1, Week 13, Week 26, Week 39 and Week 52, and presented by treatment group.

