14.5 Immunogenicity Analysis

Immunogenicity will be summarized as change from baseline as well as by study time point in subjects randomized to receive BMN 111 or placebo. Results will be summarized as

	Study 111-301 Amendment 4	Page 109
---	---------------------------	----------

incidence and titer for all cohorts. Additionally, immunogenicity may be assessed for correlations with measures of safety, PK, and efficacy.

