5.1.5 Immunogenicity

The Immunogenicity Population is defined as all subjects in the Safety Population who have at least one evaluable immunogenicity sample. Subjects randomized to one treatment group, who only receive the study drug for the other treatment group, will be analyzed in the arm of the study drug they received.

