**Study 111-301 Statistical Analysis Plan**

The mean (SD) TAb titer, number of hypersensitivity adverse events (HAEs) excluding injection site reactions, and number of subjects experiencing HAE's will be summarized by the highest HAE CTCAE Grade, and presented by TAb status (negative or positive) and treatment group.

A line graph of the mean TAb titer (+/- SD) will be presented over time for each visit by treatment group. A similar figure will be generated for NAb titers.

The change from baseline in AGV at Week 52 will be plotted against the mean TAb titer for each subject, where the mean is calculated across all post-baseline TAb titers for each subject. The Pearson correlation coefficient will be included in the figure to describe the association.

The change from baseline in AGV at Week 52 will be plotted against the mean NAb titer for each subject, where the mean is calculated across all post-baseline NAb titers for each subject. The Pearson correlation coefficient will be included in the figure to describe the association.

The relationship between immunogenicity (ADA status: negative or positive) and measures of safety and efficacy will further be presented graphically by treatment group:

- Box plot of change from baseline in AGV at week 52 by TAb status
- Box plot of change from baseline in AGV at week 52 by NAb status
- Box plot of number of hypersensitivity adverse events by TAb status
- Box plot of number of hypersensitivity adverse events (excluding ISRs) by TAb status
- Box plot of maximum severity hypersensitivity adverse event by TAb status
- Box plot of number of injection site reaction adverse events by TAb status
- Box plot of maximum duration of injection site reaction adverse event by TAb status

In addition, the following listings will be provided:

- Total antibody titers and neutralizing antibody titers
- Hypersensitivity adverse events with antibody results
- Drug-specific IgE, total IgE, C4 and serum tryptase for hypersensitivity reaction visits
- TAb cross reactivity to endogenous natriuretic peptides

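### SAP Section 19 does not limit 'Ever Positive' antibody incidence to post-baseline samples and never defines antibody status, so antibody present before dosing can be counted as incidence.

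*SAP*

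**What the plan says.** SAP Section 19 sets the sampling times: "Serum samples for anti-drug antibody (ADA) tests will be drawn pre-dose on Day 1, Week 13, Week 26, Week 39, Week 52", and then at the Safety Follow-up or Early Termination visit. TAb "positive results will be summarized for each scheduled visit, and overall (described as" 'Ever Positive'). The numerator is the "Number of subjects with a positive test result" and the denominator is the number with a non-missing TAb result. Neutralizing antibody (NAb) and cross-reactivity incidence use the same denominator and are also given by visit and overall. Titers are summarized "at Day 1, Week 13, Week 26, Week 39 and Week 52, and presented by treatment group".

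SAP Section 5.1.5 defines the Immunogenicity Population as "all subjects in the Safety Population who have at least one evaluable immunogenicity sample".

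Section 19 then relates antibodies to outcome in two ways. One plots the change in annualized growth velocity (AGV) against each child's mean titer, "where the mean is calculated across all post-baseline TAb titers for each subject". The other splits children into negative and positive, for example "Box plot of change from baseline in AGV at week 52 by TAb status". Seven box plots and one table of hypersensitivity events use such a split.

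Protocol Section 14.5 says: "Immunogenicity will be summarized as change from baseline as well as by study time point".

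**The concern.** Incidence of anti-drug antibody should describe what the drug induced. The overall rate in Section 19 carries no such limit. Nothing in the formula excludes the Day 1 sample, requires a negative Day 1 result, or requires any sample after dosing. The SAP has no category for new or boosted antibody, and Section 19 contains no change-from-baseline summary.

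Pre-existing reactivity is plausible. Protocol Section 9.4.2 describes a 39-amino-acid peptide of which 37 come from human CNP-53. Protocol Section 9.12.6.15 has baseline samples tested for NAb and for cross-reactivity with CNP, ANP and BNP. Neither section says how often reactivity occurs.

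Immunogenicity and its impact on safety, PK and efficacy is a secondary objective (Protocol Section 8, SAP Section 4.1). An overall rate that mixes pre-existing with drug-induced antibody does not answer it. The status displays have a separate gap. Positive could mean ever, at any post-baseline visit, or at Week 52, and these rules can give different groups. An unstated rule can also be chosen after unblinding.

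**Working it through.** **Reading the text**

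1. Day 1 is a scheduled antibody sample (SAP Section 19) and a derived analysis visit (SAP Table 5.4.2).
2. 'Ever Positive' spans the scheduled visits, and no visit is excluded. Literally, it includes Day 1. The SAP does not expressly say so.
3. The same section writes post-baseline for the mean titers plotted against AGV, but not for incidence or status.
4. Membership of the population needs one evaluable sample, and a Day 1 sample qualifies.
5. TAb and NAb status are used but not defined, and nothing ties them to 'Ever Positive'.

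**Size**

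The documents give no antibody prevalence or incidence, so there is no plan figure to reproduce. Two rates must be assumed:

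- b = proportion TAb positive on Day 1, taken as 0%, 2%, 5% or 10%
- t = proportion of Day 1 negatives who turn positive later, taken as 20%
- n = 55 per arm (SAP Section 4.5)

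Ever Positive = b + (1 − b) × t. Newly positive = (1 − b) × t. Share of Ever Positive already positive on Day 1 = b ÷ [b + (1 − b) × t].

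| b | Ever Positive | Children of 55 | Newly positive of 55 | Share positive before dosing |
|---|---|---|---|---|
| 0% | 0 + 1.00 × 0.20 = 20.0% | 11.0 | 11.0 | 0% |
| 2% | 0.02 + 0.98 × 0.20 = 21.6% | 11.9 | 10.8 | 0.02/0.216 = 9% |
| 5% | 0.05 + 0.95 × 0.20 = 24.0% | 13.2 | 10.5 | 0.05/0.240 = 21% |
| 10% | 0.10 + 0.90 × 0.20 = 28.0% | 15.4 | 9.9 | 0.10/0.280 = 36% |

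The share depends on t. At t = 40% it is 5%, 12% and 22% for b = 2%, 5% and 10%. At t = 0, as might hold on placebo, every 'Ever Positive' child would be a Day 1 positive.

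Boosting narrows the gap. A Day 1 positive whose titer rises enough is a genuine drug response. The gap between 'Ever Positive' and a treatment-emergent count therefore runs from zero (all boosted) to 55 × b (none boosted), which is 1.1, 2.75 or 5.5 children.

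The denominator works the other way. A Day 1-negative child with no later sample cannot show a response and lowers the rate. One such child in 55 turns 20% into 20% × 54/55 = 19.6%.

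**The case against.** The strongest defence is that the text is silent rather than wrong, and that pre-existing antibody would be visible anyway. Incidence is given by visit, titers are summarized on Day 1 and listed by child, and the placebo arm shows background reactivity. The mean-titer correlations with AGV already use post-baseline data. Prior BMN 111 use is an exclusion (Protocol Section 9.3.2), and the SAP prevails over the protocol's analysis text (Protocol Sections 14.1 and 14.8, SAP Section 4), so Protocol Section 14.5 does not bind it.

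Much of this stands. A reader of the by-visit table would see Day 1 positivity in aggregate, and the analyses are descriptive. But the aggregate row does not remove those children from the overall rate, classify any child, or say which rule defines status.

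Two stronger readings are tempting and should not be drawn:

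- That children positive only on Day 1 are placed in the positive group in the AGV and safety plots. The SAP does not say how status is derived, so they could be placed there, but no rule puts them there.
- That this pulls any antibody effect toward zero. That assumes pre-existing antibody is inert. If it is active, calling those children negative could dilute the contrast instead. The direction is not known.

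**Conclusion.** The point holds as a gap in definition. Followed literally, the overall incidence rule does not isolate drug-induced antibody, and its denominator admits children with no sample after dosing. Antibody status in the seven box plots and the hypersensitivity table is undefined.

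The size rests wholly on assumed rates: none if no child is TAb positive on Day 1, and about 9% to 36% of 'Ever Positive' children at 2% to 10% Day 1 positivity with 20% new positivity and no boosting. The primary and key secondary tests are untouched. This is an improvement worth making to a descriptive analysis of a secondary objective, and it does not threaten the trial's main conclusions.

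**What to change.** In SAP Section 19:

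- Define overall TAb and NAb incidence as treatment-emergent: Day 1 negative and positive at any post-baseline visit, or Day 1 positive with a post-baseline titer rise above a stated multiple of the Day 1 titer. Fix the multiple before unblinding. The documents give no basis for a value, so it needs its own justification.
- Use as denominator the children with a Day 1 result and at least one post-baseline result.
- For ANP, BNP and CNP-22 cross-reactivity, which are binary in the SAP's conversion table, count only a change from Day 1 negative to post-baseline positive. A titer-rise rule cannot apply.
- Keep Day 1 positivity as the by-visit row already planned.
- State that this one definition drives TAb and NAb status in every status plot and table, and label the groups accordingly.

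The cost is SAP wording and one or two derived flags from results already collected. No new sampling is needed. The headline incidence may differ slightly from the one the current wording would give.

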**Study 111-301 Statistical Analysis Plan**

The mean (SD) TAb titer, number of hypersensitivity adverse events (HAEs) excluding injection site reactions, and number of subjects experiencing HAE's will be summarized by the highest HAE CTCAE Grade, and presented by TAb status (negative or positive) and treatment group.

A line graph of the mean TAb titer (+/- SD) will be presented over time for each visit by treatment group. A similar figure will be generated for NAb titers.

The change from baseline in AGV at Week 52 will be plotted against the mean TAb titer for each subject, where the mean is calculated across all post-baseline TAb titers for each subject. The Pearson correlation coefficient will be included in the figure to describe the association.

The change from baseline in AGV at Week 52 will be plotted against the mean NAb titer for each subject, where the mean is calculated across all post-baseline NAb titers for each subject. The Pearson correlation coefficient will be included in the figure to describe the association.

The relationship between immunogenicity (ADA status: negative or positive) and measures of safety and efficacy will further be presented graphically by treatment group:

- Box plot of change from baseline in AGV at week 52 by TAb status
- Box plot of change from baseline in AGV at week 52 by NAb status
- Box plot of number of hypersensitivity adverse events by TAb status
- Box plot of number of hypersensitivity adverse events (excluding ISRs) by TAb status
- Box plot of maximum severity hypersensitivity adverse event by TAb status
- Box plot of number of injection site reaction adverse events by TAb status
- Box plot of maximum duration of injection site reaction adverse event by TAb status

In addition, the following listings will be provided:

- Total antibody titers and neutralizing antibody titers
- Hypersensitivity adverse events with antibody results
- Drug-specific IgE, total IgE, C4 and serum tryptase for hypersensitivity reaction visits
- TAb cross reactivity to endogenous natriuretic peptides

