**Study 111-301 Statistical Analysis Plan****5 GENERAL ANALYSIS CONSIDERATIONS**

The analyses described in this SAP are based on Amendment 4 of the protocol (dated 01-February-2019).

Individual subject data that is reflected in data summaries will be provided in **PI**. Unless otherwise specified, all **PI** will be by treatment group and ordered by subject number, where subject number includes the site number.

Summary tables and figures are provided by treatment group with no overall population column. There are certain exceptions (e.g. subject disposition, demographics, baseline characteristics and safety data) which are indicated in the relevant sections.

Baseline annualized growth velocity (AGV) is defined in Section 14.3.1. Baseline growth measures (other than AGV) and baseline weight are those assessed on Day 1 of dosing, regardless of timing relative to dosing. (Note: If no assessments are available, then the baseline assessment will be the last non-missing assessment prior to Day 1). All other baseline assessments are the last non-missing on-study 301 assessments prior to administration of study drug. Change from baseline is calculated as: [post-baseline value – baseline value]; Percent change from baseline is calculated as: ([post-baseline value – baseline value]/baseline value) x 100.

The Screening visit will not be presented in descriptive summaries over time. When the analysis windows have been applied (see Section 5.4), data collected at the screening visit may be included in the Baseline assessment. All assessments will be listed, but only those assessments assigned to visits according to the windows applied (see Section 5.4) will be summarized in tables or graphically. Exceptions to this are summaries of the worst post-baseline laboratory data in shift tables where all assessments are considered, and also the standing height assessments displayed in the spaghetti plots.

Unless otherwise specified, the number of subjects, mean, 25th percentile, median, 75th percentile and estimates of precision (e.g. SD, confidence interval) will be displayed to one more decimal place than the collected data. Minimum and maximum values will be presented to the same decimal places as the collected data. For summaries by visit, the number of subjects with non-missing observations (n) according to the analysis windows (see Section 5.4 for further details) at the derived visit will be presented.

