**Study 111-301 Statistical Analysis Plan**

- TAb cross reactivity by subject and cardiac disorder or HLGT 'fluid and electrolyte imbalance' related adverse event.
- Mean antibody titers and AGV

All immunogenicity listings will be ordered by treatment group, 4-digit subject number (i.e., the subject ID, excluding the site number) and visit.

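### The only antibody-efficacy coefficient is Pearson's r on raw mean titers; a log-scale or rank coefficient should stand beside it, within the BMN 111 arm

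*SAP*

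**What the plan says.** Assessing the impact of immunogenicity on efficacy is a secondary objective (protocol section 8; SAP section 4.1). Protocol section 14.5 leaves correlations optional, and SAP section 19 takes up the option:

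- Scatter plot: "The change from baseline in AGV at Week 52 will be plotted against the mean TAb titer for each subject". Each child's value is the plain average over post-baseline visits. A parallel plot uses NAb titers.
- Statistic on each plot: "The Pearson correlation coefficient will be included in the figure to describe the association".
- Scale: in the data conversion table of section 19, the column "Numerical Value for Calculation" gives negatives 0 and positives their raw titer. A separate display column gives negatives 1. No log scale, geometric mean or rank measure is mentioned.
- Other efficacy displays: "Box plot of change from baseline in AGV at week 52 by TAb status" and "Box plot of change from baseline in AGV at week 52 by NAb status", both by treatment group, and a listing, "Mean antibody titers and AGV". None of these carries an effect estimate or interval.
- General rule in SAP section 5: "Summary tables and figures are provided by treatment group with no overall population column". Exceptions are to be flagged in the section concerned, and section 19 flags none for the scatter plots.

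**The concern.** Pearson's r weights each child by the squared distance of the titer from the mean. If titers span orders of magnitude and negatives sit at 0, most of that weight falls on the few highest titers. Children with low or moderate positive titers are then almost indistinguishable from negatives. A loss of effect that depends on being positive, or on log titer, is diluted.

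At stake is the one number a reader would quote for the secondary objective. A coefficient near zero could be taken as evidence that antibodies do not matter when it partly reflects the scale.

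**Working it through.** **Inputs from the documents.** 55 children per arm, difference 1.75 cm/year, SD 2.80, two-sided 0.05 (protocol section 14.6; SAP section 4.5). SD 1.999 at 15 µg/kg over 6 months (protocol section 7.2.2), used as 2.0 for a lower SD.

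**Assumptions, because the documents give no titer data.** 20% or 45% of treated children positive; one log-normal titer per positive child with geometric mean 80 and geometric SD (GSD) 1.5, 3 or 5; loss averaging 1.75 cm/year among positives, which is the whole planned effect.

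**Step 1: the plan's own figure.** SE = 2.80 × √(2/55) = 0.534; 1.75/0.534 = 3.28; normal-approximation power = Φ(3.28 − 1.96) = 0.906; exact noncentral t gives 0.901. The stated 90% reproduces. The documents give no figure for the correlation itself.

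**Step 2: dilution by formula, same loss Δ in every positive child.** With positive fraction p, the correlation of AGV change with antibody status is −Δ√(p(1−p)) / √(σ² + Δ²p(1−p)). For p = 0.45, Δ = 1.75 and σ = 2.80 this is −0.871/√(7.84 + 0.758) = −0.297. On raw titer it is multiplied by √((1−p)/(1−p+CV²)), where CV² = exp{(ln GSD)²} − 1.

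- GSD 1.5: CV² = 0.179, factor 0.869, r = −0.258 (simulated mean −0.26).
- GSD 3: CV² = 2.34, factor 0.436, r = −0.129 (simulated mean −0.16; about 25 positives seldom show the full tail). The simulated log-titer mean is −0.28.

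**Step 3: who carries the coefficient.** The median share of the titer sum of squares held by the three highest titers is 31-51% at GSD 1.5, 71-83% at GSD 3 and 85-92% at GSD 5.

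**Step 4: simulation of the BMN 111 arm** (n = 55, 4000 runs per scenario). Detection means a negative sign with two-sided p < 0.05. It serves only as a yardstick, since no test is planned. Ranges cover 20% and 45% positive and GSD 3 and 5, at SD 2.80:

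| Loss among positives | Raw Pearson | Log Pearson | Spearman | Positive vs negative |
|---|---|---|---|---|
| Same in all | 14-23% | 41-57% | 42-55% | 44-62% |
| Proportional to log titer | 30-39% | 47-71% | 44-68% | 44-65% |
| Proportional to raw titer | 62-90% | 50-74% | 25-65% | 32-48% |

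At SD 2.0 the pattern is the same. With equal loss: raw 21-38%, log 66-85%, Spearman 66-81%. With loss proportional to raw titer: raw 74-97%, log 64-91%, Spearman 35-84%.

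**Step 5: little skew.** At GSD 1.5, equal loss and SD 2.80, raw Pearson detects 36-50%, log 42-61% and Spearman 40-54%. The disadvantage of the raw scale is then small.

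**The case against.** A reader might infer that the plan as a whole would easily miss a loss of efficacy with antibodies. The documents do not support that. The box plots by TAb and NAb status do not depend on titer scale, and the contrast they display detected an equal loss at least about as often as any coefficient. The scatter plots and the listing would also expose outlying titers. What remains is that none of these displays gives an estimate.

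A reader might also infer that the arms are pooled, so that zero-titer placebo children and the treatment effect together push r upward and hide a negative slope. The scatter-plot sentences name no arm, but the default in SAP section 5 is by treatment group and section 19 flags no exception. Only a clarification is needed.

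Nor is Pearson on raw titer wrong in general. It is the most sensitive coefficient when loss is proportional to raw titer, and replacing it with Spearman would cost sensitivity to loss concentrated at very high titers. Strong skew is assumed here, not documented.

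The log coefficient has its own limit. With negatives at 1 and TAb positives above 10, it is largely a positive-versus-negative contrast. Finally, the statistic is descriptive, and SAP section 14.1 makes anything beyond the primary analyses of the primary and key secondary endpoints non-confirmatory. All of these points stand, and they make this a minor matter.

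**Conclusion.** The point holds in limited form. The sole antibody-efficacy coefficient is sensitive to titer scale and can understate an association. With GSD 3-5 and equal loss in all positives at SD 2.80, detection by raw r is 14-23%, roughly 20 to 40 percentage points below a log or rank coefficient. The gap narrows to about 4-11 points at GSD 1.5 and reverses when loss is linear in raw titer. All of this rests on the assumed positive rate, titer distribution and shape of loss.

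Sample size is a separate limit. At SD 2.80, even the better-scaled coefficients detect complete loss of the planned effect only about 40-70% of the time under the first two loss shapes. No primary, key secondary or other confirmatory result depends on this statistic.

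**What to change.** In SAP section 19:

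- Keep both scatter plots and the raw Pearson r.
- For TAb and NAb, add either Spearman's correlation on the same subject means, which needs no new scoring rule, or Pearson on log titer. If the log version is chosen, average log titers over visits with negatives at the display value of 1, and state that this applies to these figures only.
- State that the coefficients are computed within the BMN 111 arm, in line with the by-treatment-group default.

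Optionally, give the mean difference in AGV change by antibody status with a 95% confidence interval beside the box plots. Subject-level status must then be defined, because ever-positive is defined only for the incidence table.

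The cost is a few sentences, one or two extra descriptive coefficients per figure and, for the log version, a figure-specific exception to the calculation column. No new data are needed.

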- m. A standard 12 lead ECG will include heart rate, rhythm, intervals, axis, conduction defects, and anatomic abnormalities. All ECGs will be performed in triplicate at the visits indicated in the Schedule of Events (Table 9.1.1). ECGs will be performed post-dose on study day visits at which a dose is given; in addition, on Day 1, ECGs will be performed pre-dose. On days when PK samples are being drawn, ECGs should be performed within a 5-minute window prior to 30-minute PK assessment
- n. Clinical labs (hematology, chemistry, and urinalysis) are all pre-dose collections.
- o. FSH/LH will be monitored for all subjects $>$ 8 years of age, and for subjects at Tanner stage 2 (whichever is earlier).

	Study 111-301 Amendment 4	Page 50
---	---------------------------	---------

- ^p Immunogenicity: Total and neutralizing anti-BMN 111 antibody samples (serum) will be drawn pre-dose on Day 1, Weeks 13, 26, 39, 52, and Safety Follow-Up or Early Termination visit as listed in the SOE. NAb testing and TAb testing for cross-reactivity with endogenous CNP, ANP or BNP will be performed only on Baseline and TAb positive samples. Blood (serum) samples for testing Total immunoglobulin E (IgE) and drug-specific IgE will be drawn on Day 1 and in the event of a Grade 3 or significant hypersensitivity adverse event, or at investigator or Sponsor discretion. The drug-specific IgE sample should be drawn at least 8 hr after the event start time or before the next dose. A sample for total IgE and serum tryptase should be drawn within 1 hour of the start of the event when possible or during the unscheduled safety visit.
- ^q Bone metabolism blood biomarker samples will be collected pre-dose on the indicated visits.
- ^r Bone metabolism urine biomarker samples will be collected as soon as possible upon arrival at the clinic. Each sample will be tested for biomarker concentration and creatinine concentration for normalization.
- ^s BMN 111 activity urine biomarker and urine chemistry samples will be collected pre-dose, and 1, 2, and 4 hr post-dose on the indicated visits (± 20 minutes for all urine sample time points). Each collection will be tested for biomarker concentration and urine creatinine concentration for normalization.

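### SAP 19 compares hypersensitivity events and injection site reactions by a TAb status it does not define; any status built on post-dose samples counts events before seroconversion as antibody-positive, with no adjustment for time at risk

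*SAP*

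**What the plan says.** **Sampling.** SAP Section 19 states: "Serum samples for anti-drug antibody (ADA) tests will be drawn pre-dose on Day 1, Week 13, Week 26, Week 39, Week 52", and adds a sample at the Safety Follow-up or Early Termination visit. Protocol Table 9.1.1 (immunogenicity footnote) has the same schedule: "Total and neutralizing anti-BMN 111 antibody samples (serum) will be drawn pre-dose on Day 1, Weeks 13, 26, 39, 52", again with the follow-up or early termination sample. The first scheduled post-dose sample is therefore at Week 13; an earlier one arises only if a child leaves before then.

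**Displays.** The same SAP section says: "The relationship between immunogenicity (ADA status: negative or positive) and measures of safety and efficacy will further be presented graphically by treatment group". The list that follows includes "Box plot of number of hypersensitivity adverse events by TAb status", the same count without ISRs, the worst severity of a hypersensitivity event, "Box plot of number of injection site reaction adverse events by TAb status" and "Box plot of maximum duration of injection site reaction adverse event by TAb status". A table in the section also breaks down hypersensitivity events (ISRs excluded) by TAb status and arm.

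**Status.** No rule is given for assigning a child to negative or positive in these displays. The only subject-level rule in the section belongs to the incidence table, where positive results are "summarized for each scheduled visit, and overall (described as 'Ever Positive".

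**Event window.** Adverse events are collected from the first dose (protocol 10.2.1). SAP 19 gives only an end to the window: "Summary tables will include all safety events up to 30 days following treatment discontinuation". Nothing starts the count at a positive sample, splits follow-up by sample, or divides these counts by time.

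**The concern.** Dosing is daily from Day 1, while antibody status becomes visible only at quarterly samples. If a child who first tests positive at Week 26 or 39 is plotted as positive, all reactions since Day 1 go with that label, including those that occurred before any antibody existed. If antibodies do raise the reaction rate, the contrast is diluted, and more so if reactions cluster in the first weeks. In the other direction, a child followed for longer has more time both to turn positive and to accumulate events, which creates an association where there is none.

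The displays serve a stated secondary objective, the impact of immunogenicity on safety (protocol Section 8, SAP 4.1). Protocol 7.5.2.2 names ISRs as an identified risk, and hypersensitivity including antibody development as a potential one. A flattened contrast could be read as reassurance on exactly that question.

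**Working it through.** The plan states no figure on this point, so there is none to reproduce. The documents give no seroconversion rate, event rate, event timing or dropout; those are assumptions below.

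**Step 1. Does the structure force the misalignment?** A box plot of per-child counts or maxima needs one status per child. The candidate rules are:
- ever positive, last sample positive, or Week 52 positive: each uses post-dose samples, so events before conversion fall in the positive group;
- Day 1 status only: avoids this, but cannot describe antibodies that arise on treatment.

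Showing the plots by treatment arm does not help, because the misalignment lies within the BMN 111 arm.

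**Step 2. Dilution at a constant background rate.** Inputs: 52 weeks of daily treatment (SAP 4.4) and samples at Weeks 13, 26, 39 and 52 (SAP 19). Let *s* be the week of conversion and RR the true rate ratio afterwards. For full follow-up, the ratio of a positive child's expected count to that of a never-positive child is

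(s + RR × (52 − s)) / 52.

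| s | RR = 2 | RR = 3 |
|---|---|---|
| 0 | 104/52 = 2.00 | 156/52 = 3.0 |
| 13 | (13 + 78)/52 = 1.75 | (13 + 117)/52 = 2.5 |
| 26 | (26 + 52)/52 = 1.50 | (26 + 78)/52 = 2.0 |
| 39 | (39 + 26)/52 = 1.25 | (39 + 39)/52 = 1.5 |

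A first positive at Week 13 means conversion somewhere in Weeks 0-13, and so on. The observed ratio is therefore a range:

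| First positive sample | True doubling | True tripling |
|---|---|---|
| Week 13 | 1.75-2.00 | 2.5-3.0 |
| Week 26 | 1.50-1.75 | 2.0-2.5 |
| Week 39 | 1.25-1.50 | 1.5-2.0 |

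**Step 3. Front-loaded reactions (assumption: Weeks 0-13 carry 3 times the later rate).** Background exposure becomes 3 × 13 + 39 = 78 units. A doubling from *s* = 13, 26 and 39 shows as (39 + 2 × 39)/78 = 1.50, (52 + 2 × 26)/78 = 1.33 and (65 + 2 × 13)/78 = 1.17. The ranges for a first positive at Week 13, 26 or 39 fall to 1.50-2.00, 1.33-1.50 and 1.17-1.33.

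**Step 4. Both effects together, by simulation.** Assumptions: nobody positive on Day 1; exponential time to conversion, with 20-60% converted by Week 52; lasting positivity; a sample on leaving early; dropout uniform over the year; early rate 1 or 3 times the later rate. Ratio of mean counts, ever-positive to never-positive:

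| Dropout | No true effect | True doubling |
|---|---|---|
| 0% | 1.00 | 1.39-1.57 |
| 10% | 1.03-1.07 | 1.44-1.69 |
| 20% | 1.07-1.15 | 1.48-1.80 |

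At a constant background rate, 43-61% of ever-positive children's events precede their first positive sample, but only 27-48% truly precede conversion. With the threefold early rate the shares are 59-75% and 39-61%. No figure is offered for maximum severity or maximum duration.

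**The case against.** The strongest case is that this matters little and is partly covered. The plots carry no test, the safety analysis is descriptive (protocol 14.4), and protocol 14.5 makes correlation of immunogenicity with safety optional. SAP 19 already lists hypersensitivity events with antibody results and orders its listings by child and visit, so the sequence can be traced case by case. SAP 15.1.2 gives exposure-adjusted ISR and hypersensitivity rates and a profile of ISR timing. All of that is true, and it limits the severity. But the exposure-adjusted tables are by arm, not by antibody status, and a listing is not a comparison. No event-with-antibody listing is named for ISRs, which were among the most common events in Study 111-202 (protocol 7.2.2). A significant hypersensitivity event triggers IgE and tryptase samples, not TAb (protocol 9.12.6.16).

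A reader might also infer more than the documents support:
- *That the SAP fixes each child as ever positive in these plots.* It does not say so. A single status is an inference, though a firm one (Step 1); what is documented is a missing definition.
- *That a doubling would show as exactly 1.75, 1.50 or 1.25.* Those are the most diluted ends, reached only if conversion falls on the sampling day.
- *That children who leave early go unsampled, so follow-up bias is large.* An Early Termination sample is scheduled, and children who stop treatment are encouraged to keep to the visit schedule (protocol 9.3.4). In the scenarios above the spurious excess is small.

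**Conclusion.** The point holds as a gap in definition and alignment. SAP 19 does not say what TAb status means for the safety displays, and every rule that uses post-dose samples puts some events from before conversion in the positive group, without adjustment for time at risk. The dilution follows from the design whenever there is a true effect. Its size depends on when children convert and when reactions occur, which the documents do not give: for a doubling, from almost none (conversion soon after Day 1) to 1.25 (conversion at Week 39), and closer to 1 if reactions are front-loaded. Unequal follow-up pushes the other way, by about 1.03-1.15 with 10-20% assumed dropout and no true effect, so the net bias has no fixed direction.

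The severity is minor to moderate. A reader should not infer that the efficacy conclusions or the main adverse event tables are affected: the displays are descriptive and do not enter the primary or key secondary analyses.

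**What to change.** In SAP Section 19:

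1. Define TAb status for every safety display that uses it, and say how children positive on Day 1 are classified.
2. For the BMN 111 arm, add one table of exposure-adjusted rates of hypersensitivity events (with and without ISRs) and of ISRs, by TAb status within each interval between samples: Day 1 to Week 13, 13 to 26, 26 to 39, 39 to 52. Classify each interval by the result at its start and, as a bound, by the result at its end. Comparing within an interval also removes the effect of early clustering.
3. Extend the event-with-antibody listing to ISRs.
4. Keep the planned box plots as a supplement.

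The cost is one table and one listing from event dates and titers already collected. There are limits. Conversion is known only to within about 13 weeks, so the start rule counts some events after conversion as negative and the end rule counts some before it as positive; showing both brackets the uncertainty. The first interval will have few children positive at its start. With 55 planned in the BMN 111 arm, cells for hypersensitivity other than ISRs may be sparse.
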